7.4.3 Clinical Laboratory Assessments

Blood and urine samples will be collected for the following clinical laboratory tests, following the timing noted in the Schedule of Assessments for Part 1 and Part 2 (Table 1). All samples should be clearly identified.

The Sponsor should receive a list of laboratory normal ranges before shipment of the IMP. Any change in laboratory normal ranges during the study should be forwarded to the Sponsor or its designee.

The laboratory variables to be assessed for safety evaluations are provided in Table 4. Unscheduled retest of laboratory safety tests at the discretion of the investigator are permitted during screening and throughout the study.

Table 4 Clinical Laboratory Evaluations^a

Biochemistry	Aspartate aminotransferase Alanine aminotransferase Alkaline phosphatase γ-Glutamyltransferase Lactate dehydrogenase Creatine phosphokinase	Bilirubin (total) Protein (total) Albumin α-1-acid glycoprotein Cholesterol Triglycerides Amylase Lipase Uric acid	Sodium Potassium Chloride Bicarbonate Calcium Magnesium Phosphate Creatinine Urea Glucose
Hematology	Hematocrit Hemoglobin Red blood cell count Mean corpuscular volume Mean corpuscular hemoglobin Mean corpuscular hemoglobin concentration	Platelet count White blood cell count	White blood cell differentials and absolute counts: Basophils Eosinophils Lymphocytes Monocytes Neutrophils
Coagulation	International Normalized Ratio (INR)		
Other Tests	Hepatitis B surface antigen Hepatitis B core antibody Hepatitis C antibody Human immunodeficiency virus I and II antibodies	Cotinine Alcohol (breathalyzer) Follicle-stimulating hore (for postmenopausal w	
Urinalysis	pH Nitrite Protein Glucose	Ketone bodies Urobilinogen Bilirubin Leukocyte esterase Blood	
Urine Microscopy ^b			
Urine Drug Screen ^c	Cocaine Amphetamines Methamphetamines Opiates	Barbiturates Ecstasy Benzodiazepine Methadone	Cannabinoids (THC) Phencyclidine Oxycodone Tricyclic antidepressants

- Subjects should fast for 8 hours prior to clinical laboratory blood sample collection.
- b Only if blood, protein, nitrite, or white blood cell count is positive on the dipstick.
- For all subjects, a negative cannabinoid (THC) result on drugs of abuse screening is required to participate in the study. If the result is positive, the Principal Investigator may request to repeat the test. For subjects with hepatic impairment, a positive cannabinoid (THC) result on drugs of abuse screening will not be exclusionary (at Screening or Day -1) if the hepatic-impaired subject uses cannabinoids on medical recommendation. In subjects with hepatic impairment, positive test for drugs used on medical recommendation will be not exclusionary.

The total blood volume to be drawn from each subject for planned assessments during the study will not exceed the volume of a standard donation (approximately 450 mL) and will be specified in the laboratory manual.

7.4.4 Vital Signs, Physical Examinations, and Other Assessments

7.4.4.1 Vital Signs

Vital signs, including oral temperature, systolic and diastolic blood pressure, and pulse rate will be assessed as per the timepoints specified in the Schedule of Assessments for Part 1 and Part 2 (Table 1).

A semi-automated pulse rate and blood pressure recording device with an appropriate cuff size will be utilized. The pulse rate and blood pressure will be measured after 10 minutes rest in the semi-supine position (supine at timepoints where the assessment coincides with 12-lead ECG assessment) with the subject's arm unconstrained by clothing or other material. The blood pressure should be assessed on the same arm for each subject throughout the study.

7.4.4.2 Physical Examination

Complete physical examinations will be performed at the timepoints specified in the Schedule of Assessments for Part 1 and Part 2 (Table 1) and will include an assessment of: general appearance, skin, head and neck, lymph nodes, thyroid, abdomen, and musculoskeletal, cardiovascular, respiratory, and neurological systems.

Body weight will be measured at Screening and at Day -1. Height will be measured at Screening only.

All clinically significant abnormalities occurring before signature of informed consent should be recorded in the medical history and/or disease history section of the eCRF; all abnormalities occurring or worsening after the subject signed the Informed Consent Form should be recorded in the AE section of the eCRF.

7.4.4.3 Electrocardiograms

Standard 12-lead ECGs will be performed at the timepoints specified in the Schedule of Assessments for Part 1 and Part 2 (Table 1) after 10 minutes rest in the supine position. Only the overall evaluation (normal/abnormal) will be recorded in the eCRF, and if abnormal, the specific abnormality will be recorded. Abnormal evaluations will be judged as clinically significant or not clinically significant by the Investigator. The ECG recordings must be performed before PK sampling timepoints on days where both assessments are performed.

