 - PK profile of the major tepotinib metabolites MSC2571109 and MSC2571107 (plasma) in terms of AUC_{0-t} , $AUC_{0-\infty}$, C_{max} , t_{max} , $t_{1/2}$, $AUC_{extra\%}$ at Day 1 to Day 15 (healthy subjects) or Day 22 (hepatic impaired subjects) calculated by noncompartmental analyses, and $MRAUC_{0-\infty}$ and MRC_{max}
- Occurrence of treatment-emergent adverse events, changes from baseline in laboratory safety tests, 12-lead electrocardiograms (ECG) morphology and time intervals (PR, QRS, RR, QT and corrected QT intervals using Fridericia's formula [QTcF]), and vital signs.

Pharmacokinetics: Blood samples for PK analysis will be collected on Day 1 predose and 0.25, 0.5, 0.75, 1.0, 1.5, 2.0, 3.0, 4.0, 6.0, 8.0, 10.0, 12.0, and 16.0 hours postdose, Day 2 at 24, 30, and 36 hours postdose, Day 3 at 48, 54, and 60 hours postdose, Day 4 (72 hours), Day 5 (96 hours), Day 6 (120 hours), Day 7 (144 hours), Day 8 (168 hours), Day 10 (216 hours), Day 13 (288 hours), Day 15 (336 hours), and Day 22 (504 hours postdose; hepatic impaired subjects only).

Other assessments: Throughout the study at specified timepoints treatment-emergent adverse events, changes from baseline in laboratory safety tests, 12-lead ECG morphology and time intervals (PR, QRS, RR, QT and QTcF), and vital signs will be assessed.

12/75

Diagnosis and key inclusion and exclusion criteria: Men and women (of nonchildbearing potential), 18 to 75 years (inclusive) of age, with a body mass index of 18 to 36 kg/m² (inclusive) and a body weight \geq 50 kg at Screening, with the absence of acute hepatitis or HIV 1 and 2, who have given informed consent and are willing and able to comply with study procedures will be eligible for enrollment. Subjects with impaired hepatic function (Child-Pugh class A or Child-Pugh class B) and subjects with normal hepatic function will be eligible to enroll in the study. Healthy subjects will be excluded if they have hepatitis B or C or had a previous infection with hepatitis C treated with Sofosbuvir or other antiviral compounds, or any other clinically relevant disease, as considered by the Investigator. Subjects with impaired hepatic function will be excluded if they have primary biliary liver cirrhosis, nonstabilized chronic heart failure, hepatocarcinoma, hepatic encephalopathy (Grade III or IV), sepsis or gastrointestinal bleeding, or any other clinically relevant disease, as considered by the Investigator.

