8.1 Sample Size

Pharmacokinetic studies including subjects with impaired hepatic function are usually exploratory by nature. Considering the CVs for the primary endpoints AUC_{0-t} and C_{max} of tepotinib, 20.4% and 22.8% respectively (Study EMR200095-007), 6 evaluable subjects per group will provide 80% power for detecting a group difference of 44% (AUC_{0-t}) and 50% (C_{max}), which is considered

sufficient to meet the study objectives having the therapeutic window of tepotinib in mind. The significance level was set to 0.05 two-sided.

Therefore, 18 subjects (3 groups x 6 subjects) should be included in Part 1 and 6 subjects in Part 2. Drop-outs will be replaced only if they cannot provide an evaluable PK profile.

Randomization 8.2

Not applicable.

8.3 **Endpoints**

8.3.1 **Primary Endpoints**

• PK profile of tepotinib (plasma) in terms of AUC_{0-t}, AUC_{0-∞}, and C_{max} at Day 1 to Day 15 (healthy subjects) or Day 22 (hepatic impaired subjects) calculated by noncompartmental analyses.

8.3.2 **Secondary Endpoints**

• PK profile of tepotinib (plasma) in terms of t_{max}, t_{1/2}, CL/f, V₇/f, AUC_{extra}% at Day 1 to Day 15 (healthy subjects) or Day 22 (hepatic impaired subjects) calculated by noncompartmental analyses

PK profile of the major tepotinib metabolites MSC2571109 and MSC2571107 (plasma) in terms of AUC_{0-t}, AUC_{0-∞}, C_{max}, t_{max}, t_{1/2}, AUC_{extra%} at Day 1 to Day 15 (healthy subjects) or Day 22 (hepatic impaired subjects) calculated by noncompartmental analyses, and MRAUC_{0-∞} and MRC_{max}

• Occurrence of TEAEs, changes from baseline in laboratory safety tests, 12-lead ECG morphology and time intervals (PR, ORS, RR, OT and OTcF), and vital signs.

8.3.3 **Other Endpoints**

Not applicable.

8.4 **Analysis Sets**

Screening Analysis Set

The Screening Analysis Set will include all subjects who provide signed informed consent, regardless of treatment status in the trial. This analysis set will be used for subject disposition.

Safety Analysis Set

The Safety Analysis Set will include all subjects who receive study treatment. All safety analyses will be based on this analysis set.

Pharmacokinetic Analysis Set

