Clinically significant, abnormal findings from the physical examination are to be reported as AEs. Separate summaries of the physical examination will not be provided. Vital signs and 12-lead ECG data will be summarized for observed and change-from-baseline values by hepatic function group and timepoint using descriptive statistics. Clinically noteworthy 12-lead ECG findings for individual subjects will be listed and summarized as appropriate.

8.6 **Interim and Additional Planned Analyses**

An SMC may be established to evaluate the safety and PK results of Part 1 and provide recommendations on the tepotinib dose and population to be enrolled in Part 2 if the overall development program of tepotinib decides to use higher doses than 500 mg (up to 1000 mg) in the Phase 2 or Phase 3 studies. Details regarding the SMC responsibilities are provided in Section 5.1.

No additional planned analyses are scheduled.

9 **Ethical and Regulatory Aspects**

9.1 **Responsibilities of the Investigator**

The Investigators are responsible for the conduct of the study at the study centers and will ensure that the study is performed in accordance with this protocol, the ethical principles outlined in the Declaration of Helsinki, ICH GCP, and any other applicable regulations. The Investigators must ensure that only subjects who have given informed consent are included in the study.

According to United States Code of Federal Regulations Part 54.2 (e), for studies conducted in any country that could result in a product submission to the United States FDA for marketing approval and could contribute significantly to the demonstration of efficacy and safety of an IMP (which are considered "covered clinical trials" by the FDA), the Investigator and all subinvestigators are obliged to disclose any financial interest which they, their spouses or their dependent children may have in the Sponsor or the Sponsor's product under study. This information is required during the study and for 12 months following completion of the study.

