9.6 Institutional Review Board

Prior to commencement of the study at a given center, this clinical study protocol will be submitted together with its associated documents (Subject Information, Informed Consent Form, Investigator's Brochure, subject card) to the responsible IRB for its favorable opinion or approval, which will be filed in the Investigator Site File. A copy will be filed in the Sponsor Trial Master File at the CRO.

The IRB will be asked to document the date of the meeting at which the favorable opinion or approval was given and the members and voting members present. Written evidence of favorable opinion or approval that clearly identifies the study, the clinical study protocol version and the Subject Information and Informed Consent Form version reviewed should be provided. Where possible, copies of the meeting minutes should be obtained.

Amendments to this clinical study protocol will also be submitted to the concerned IRB, before implementation of substantial changes (see Section 10.5). Relevant safety information will be submitted to the IRB during the course of the study in accordance with national regulations and requirements.

9.7 **Health Authorities**

The clinical study protocol and any applicable documentation (ie, Investigational Medicinal Product Dossier, Subject Information and Informed Consent Form) will be submitted or notified to the Health Authorities in accordance with all local and national regulations for each study center.

10 **Study Management**

10.1 **Case Report Form Handling**

Refer to the manual of operations for eCRF handling guidelines.

The main purpose of the eCRF is to obtain data required by the clinical study protocol in a complete, accurate, legible and timely manner. The data in the eCRF should be consistent with the relevant source documents

The Investigator or designee is responsible for ensuring that the data collected in the course of this study is accurate and documented appropriately on all applicable forms. They will then be processed, evaluated, and stored in anonymous form in accordance with applicable data protection regulations. The Investigator must ensure that the eCRFs and any other associated documents forwarded to the Sponsor or its designated organization contain no mention of any subject names.

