The data will be entered into a validated database. The Sponsor or its designee will be responsible for data processing, in accordance with the Sponsor's data management procedures. Database lock will occur once quality control and quality assurance procedures have been completed. PDF files of the eCRFs will be provided to the Investigators at the completion of the study.

The eCRFs are essential study documents and must be suitable for regulatory inspections and submissions.

Source Data and Subject Files 10.2

The Investigator must keep a file (medical file, original medical records) on paper or electronically for every subject in the study. It must be possible to identify each subject by using this subject file. This file will contain the demographic and medical information for the subject listed below and should be as complete as possible:

Tepotinib (MSC2156119J) Tepotinib Hepatic Impairment Trial MS200095-0028

- Subject's full name, date of birth, sex (gender), height, weight
- Medical history and concomitant diseases
- Prior and concomitant therapies (including changes during the study)
- Study identification, that is, the Sponsor study number for this clinical study, and subject number
- Dates for entry into the study (informed consent) and visits to the study center
- Any medical examinations and clinical findings predefined in this clinical study protocol
- All AEs
- Date that the subject left the study including any reason for early study discontinuation or withdrawal from IMP (if applicable).

All documents containing source data must be filed, including, but not limited to computed tomography or magnetic resonance imaging scan images, ECG recordings, and laboratory results. Such documents must bear the subject number and the date of the procedure. If possible, this information should be printed by the instrument used to perform the assessment or measurement. As necessary, medical evaluation of such records should be performed; all evaluations should be documented, signed, and dated by the Investigator.

The Monitor will be trained to use the electronic database / eCRF and will have read-only access to the study data in the eCRF for source data verification. Data reviewed can be signed off and queries issued directly in the eCRF.

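### Section 7.4.4.3 restricts ECG data in the eCRF to a normal/abnormal evaluation, while a secondary endpoint is change from baseline in PR, QRS, RR, QT and QTcF

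*Protocol*

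**What the plan says.** **Endpoint.** The Synopsis lists, among the assessments to be made through the study, changes from baseline in "12-lead ECG morphology and time intervals (PR, QRS, RR, QT and QTcF", with QTcF by Fridericia's formula. The Synopsis list of secondary endpoints and Section 8.3.2 (Secondary Endpoints) contain the same item. In the machine-read text of Section 8.3.2 some letters Q appear as O; that is a reading artefact and no fault of the plan.

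**Analysis.** Section 8.5.4 (Analysis of Safety and Other Endpoints) states: "Vital signs and 12-lead ECG data will be summarized for observed and change-from-baseline values by hepatic function group", by timepoint and with descriptive statistics. A separate sentence deals with listing noteworthy ECG findings in individual subjects.

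**Data capture.** Section 7.4.4.3 (Electrocardiograms) states: "Only the overall evaluation (normal/abnormal) will be recorded in the eCRF, and if abnormal, the specific abnormality will be recorded". The only other item it describes is also categorical: "Abnormal evaluations will be judged as clinically significant or not clinically significant by the Investigator".

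**Data handling.** Section 10.1 (Case Report Form Handling) says: "The main purpose of the eCRF is to obtain data required by the clinical study protocol". Section 10.2 (Source Data and Subject Files) includes ECG recordings among the source documents that must be filed.

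**The concern.** The endpoint and its analysis need numbers, and the capture rule admits only categories. A site that follows Section 7.4.4.3 to the letter enters no interval in milliseconds for any subject at any visit, baseline included.

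Safety and tolerability in hepatic impairment is a stated secondary objective (Section 4.2), and the intervals are a named part of its endpoint. A normal/abnormal flag cannot show a rise in QTcF or PR that stays within the normal range, nor allow the size of such changes to be compared between the Child-Pugh groups and the healthy controls. Section 8.5.1 evaluates data as observed with no imputation, so intervals that are not captured simply stay missing.

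**Working it through.** The plan gives no figure to reproduce here. The check sets the sections against each other and then counts the ECGs affected.

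**1. What the endpoint needs and what the eCRF receives**

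| Item | Required by Synopsis / Section 8.3.2 | Provided for in Section 7.4.4.3 |
|---|---|---|
| Morphology | yes | yes: overall evaluation, named abnormality, clinical significance |
| PR, QRS, RR, QT | yes, as change from baseline | no numeric entry |
| QTcF | yes, as change from baseline | no numeric entry, and not derivable, since QT and RR are absent |

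The eCRF thus receives 0 of the 5 named intervals as numbers.

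**2. Does Section 8.5.4 need numbers?** It names no interval. It does ask for observed and change-from-baseline values with descriptive statistics, in one sentence covering vital signs and ECG together, and it treats noteworthy findings separately. Read with the endpoint, that sentence requires numeric intervals.

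**3. Is there another route into the database?**
- Section 2 names a central laboratory for clinical laboratory tests and a testing laboratory for PK samples. It names nobody for ECGs.
- Section 10.1 describes entry through the eCRF and mentions no ECG transfer.
- Section 10.2 keeps the tracings as source only.
- Appendix III records no change to Section 7.4.4.3, so the sentence is current text.

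The protocol states no route.

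**4. How many ECGs are affected?** In the legible part of Table 1, 12-lead ECGs are marked at 48, 72, 168, 336 and 504 h. Footnote k makes the 336 h visit (Day 15) the End of Study visit for healthy subjects only and limits that visit in impaired subjects to PK, adverse events and concomitant therapy. Footnote l restricts 504 h to impaired subjects.

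- Healthy: 48, 72, 168, 336 h = 4 ECGs per subject
- Impaired: 48, 72, 168, 504 h = 4 ECGs per subject
- Part 1: 6 × 4 + 12 × 4 = 72 ECGs
- With the optional Part 2: 72 + 6 × 4 = 96 ECGs
- Four measured quantities per ECG (RR, PR, QRS, QT): 72 × 4 = 288 values; 96 × 4 = 384 values

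QTcF comes on top, as a derived value. These are minimum counts: the part of Table 1 from Screening to Day 2 is broken in the text at hand, so baseline and early postdose ECGs are left out.

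**The case against.** The best reply is that Section 7.4.4.3 limits only what goes into the eCRF. It does not say that intervals are not measured or stored. It could be read as confining the investigator's manual entry to the interpretation, with machine-measured intervals arriving electronically under a manual or data management procedure that is not shown. The protocol does not describe how PK concentrations reach the database either, and Section 10.1 gives only the main purpose of the eCRF, so not every required value need pass through it. The stakes are also modest: the endpoint is descriptive, no sample size rests on it, each subject receives a single dose, and an interval outside normal limits can still be entered as the specific abnormality.

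Much of this stands. An external transfer is not logically excluded, and Section 10.1 alone does not prove the point. The values can be recovered from source, and what would be lost is mainly shifts within the normal range. The comparison with PK and laboratory data does not carry over, however. Those data have named laboratories and no sentence restricting their capture. ECG data have a restrictive rule and no named provider. Even if a transfer exists, the protocol gives sites no instruction to capture intervals, and its sections still disagree.

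**Conclusion.** The concern holds. It is an inconsistency within the protocol: an explicit capture rule defeats an explicit secondary endpoint. A statistical analysis plan cannot cure it, because it can define summaries but cannot supply values that were never recorded. At least 288 measured values in Part 1, or 384 with Part 2, have no stated way into the database. These counts measure the volume of data affected, not bias or loss of power.

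The conclusion assumes that no document outside the protocol arranges an ECG transfer; if one does, the data exist and the defect is one of wording. The morphology part of the endpoint and the primary PK analysis are not affected. The point should be fixed but does not threaten the main purpose of the trial.

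**What to change.** Preferred: replace the restrictive sentence in Section 7.4.4.3 so that RR (or heart rate), PR, QRS and QT are entered in the eCRF or transferred electronically for every scheduled 12-lead ECG, baseline included, with QTcF recorded or derived. Keep the overall evaluation, the named abnormality and the judgement of clinical significance.

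Alternative: if the intervals are not meant to be analysed, delete them from the Synopsis and Section 8.3.2 and limit Section 8.5.4 to categorical ECG summaries.

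The preferred change costs about four extra data fields per ECG, or one electronic transfer. It uses tracings already made and filed as source and adds no procedure for subjects.

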7.5 Pharmacokinetics

7.5.1 Body Fluids

Blood samples for the PK evaluation of tepotinib and its metabolites (MSC2571109 and MSC2571107) in plasma will be collected at the timepoints specified in the Schedule of Assessments for Part 1 and Part 2 (Table 1). The exact date and time of sample collection will be recorded in the eCRF. Samples not collected at the exact timepoint are not to be considered

47/75

protocol deviations as long as the actual collection date and time is recorded. Every effort should be made to collect samples at the appropriate timepoint.

Details of the sample collection, blood volume, labeling, storage and shipment requirements will be provided in a separate manual of operations or laboratory manual.

The PK sampling is planned differently for healthy subjects than for hepatic impaired subjects as a different half-life is expected. As the majority of healthy subjects do not have measureable concentrations after Day 15, PK sampling until Day 15 is considered sufficient. As the optimal sampling schemes of the hepatic impairment group is difficult to predict, an additional sampling time of 1 week (up to Day 22) is considered to be sufficient. The SMC may decide on a different sampling scheme for Part 2.

All sample analyses will be performed using a validated method measuring parent drug and metabolites.

The free fraction of tepotinib will be determined to assess a potential effect of low serum albumin concentration which might result in an increased free fraction of tepotinib in subjects with hepatic impairment.

